## 11.2.1 Analytical method

The assay of RPH-104 and anti-drug antibodies in blood serum will be carried out using a validated analytical procedure. The lower limit of quantification (LLoQ) of RPH-104 will not be higher than 5% of Cmax.

# 11.3 Assessment of pharmacodynamics

Serum levels of hs-CRP, amyloid protein, and cytokine levels (IL-1 $\alpha$ , IL-1 $\beta$ , IL-1RA, IL-6, IL-8, TNF- $\alpha$ ) are assessed in all randomized patients.

The time windows for blood sampling to assess levels of hs-CRP, serum amyloid A protein, and cytokine levels (IL-1 $\alpha$ , IL-1 $\beta$ , IL-1RA, IL-6, IL-8, TNF- $\alpha$ ) in serum is presented in Table 3.1.

The methods used to collect blood samples, obtain plasma, and store samples are described in the guideline for laboratory tests.

Serum samples to assess hs-CRP, serum amyloid protein A, and cytokine levels are sent to the Unimed central laboratory. The shipment handling procedure is described in the laboratory manual.

# 11.4 Efficacy assessment

## 11.4.1 Measurement of pain intensity in the assessed joint

To assess pain intensity, an affected joint with the maximum pain intensity on Day 1 is selected.

Pain intensity is assessed in all patients using a 100 mm VAS. Pain intensity assessments are carried out before the start of therapy with the investigational products, at 15, 30, 45 minutes, 1, 1.5, 2, 4, 8, 24, 48, 72 hours, 5, 6, 10, 15, 18, 22, 29 and 45 days after the start of the investigational product use. In case of the use of the rescue medication, pain intensity must be assessed before its administration.

For each assessment of pain intensity, the patient records the result of the assessment in the patient questionnaire.

Completed questionnaires should be dated with indication of time and signed by the patient.

When handing over the questionnaires to patients outside the study site, the investigator will instruct them on proper completion.

Patient questionnaires and instructions for completion are provided in a separate document.

## 11.4.2 Patient global assessment of efficacy

All randomized patients evaluate the efficacy of their prescribed therapy. The patients perform global assessment of efficacy at 15, 30, 45 minutes, 1, 1.5, 2, 4, 8, 24, 48, 72 hours, 5, 6, 10, 15, 18, 22, 29 and 45 days after the start of the investigational product use. In case of the use of the rescue medication, global assessment of efficacy must be carried out before its administration.

For global assessment of efficacy, patients use a categorical scale with 5 response options. For each assessment of response to therapy, the patient records the result of the assessment in the patient questionnaire.

Completed questionnaires should be dated with indication of time and signed by the patient.

CONFIDENTIAL P. 62 of 84

When handing over the questionnaires to patients outside the study site, the investigator will instruct them on proper completion.

Patient questionnaires and instructions for completion are provided in a separate document.

# 11.4.3 Assessment of the degree of swelling, tenderness, and erythema in the assessed joint by physician

The severity of edema, tenderness, erythema in the assessed joint is assessed for all randomized patients at the time points indicated in Table 3.1. For assessment, categorical scales are used in accordance with the "Form for Assessment of the Degree of Swelling, Tenderness, Erythema and Movement Restriction in the Assessed Joint" (see Appendix 2) with the following response options:

# **Swelling assessment:**

- "absence" no swelling
- "mild" palpable swelling
- "moderate" visible swelling
- "severe" bulging outside the joint

#### **Tenderness assessment:**

- "absence" no tenderness
- "mild" tenderness when touched
- "moderate" pain and flinching
- "severe" pain, flinching and withdrawal of the limb

### **Erythema assessment:**

- absence
- presence
- unevaluable

The assessment results are recorded in the source documentation and eCRF.

# 11.4.4 Assessment of the degree of movement restriction in the assessed joint by physician

The investigator evaluates the range of motion in the assessed joint for all randomized patients at the time points indicated in Table 3.1. For assessment, a 5-point categorical scale is used in accordance with the "Form for Assessment of the Degree of Swelling, Tenderness, Erythema and Movement Restriction in the Assessed Joint" (see Appendix 2) with the following response options:

- 1. Normal range,
- 2. Slightly limited range,
- 3. Moderately limited range,
- 4. Significantly limited range,
- 5. Joint movement is impossible.

#### 11.4.5 Assessment of the amount of the rescue medication used by the patient

All cases of the use of the rescue medication are recorded in the source documentation and CRF. The name, date, time and dose of the rescue medication used are recorded.

CONFIDENTIAL P. 63 of 84

#### 11.4.6 Health assessment questionnaire (HAQ) assessment

At visits on Day 1 (pre-randomization), Day 15, Day 29, and Day 45, patients are given the HAQ for self-completion.

The HAQ with instructions for completion is provided in a separate document.

# 11.5 Safety and tolerability assessment

#### 11.5.1 Adverse event assessment

The assessment of adverse events is described in Section 12.

## 11.5.2 Assessment of injection site reactions

The presence of local reactions to the administration of the investigational product is assessed in patients who received RPH-104 at the time points indicated in Table 3.1. The Investigator assesses the presence of tenderness, redness, swelling, induration, hemorrhage and itching at the RPH-104 injection site. All cases of RPH-104 injection site must be followed-up until resolution.

# 11.5.3 Physical examination

Physical examination should be carried out in accordance with the study procedure schedule (see Section 3). Information about the completed physical examination and examined organ systems should be described in the source documents kept at the study site. Any abnormalities in physical examination findings obtained before the first self-administration of the investigational medicinal product should be recorded in the CRF, in the 'Concomitant diseases' section. Any abnormalities in physical examination findings obtained after the first self-administration of the investigational medicinal product and meeting the definition of an adverse event should be recorded in the CRF, in the 'Adverse events' section.

The CRF will have no section to record normal findings of periodic physical examinations; however, such results should be reflected in the source documents.

Complete physical examination includes: assessment of overall health, skin (presence of rash or lesions), head, mouth, eyes, ears, throat, nose, lungs (auscultation), heart (auscultation for murmurs, gallop rhythm, pericardial friction rubs), lower extremities (peripheral edema, presence of varicose veins), abdomen (palpation and auscultation), nervous system (mental status, gait, reflexes, motor and sensory functions, coordination) and lymph nodes.

#### 11.5.4 Assessment of vital signs

Vital signs include: body temperature, pulse rate, respiratory rate, and sitting blood pressure measured after 5-minute rest. The Day 1 data obtained before the first dose of the investigational product are regarded as baseline vital signs. On subsequent days, vital signs should be evaluated and registered prior to the administration of Voltaren® (diclofenac) in patients treated with Voltaren® (diclofenac).

Clinically significant abnormalities in vital signs are to be recorded as adverse events.

# 11.5.5 Electrocardiography

A 12-lead electrocardiography should be carried out in accordance with the study flow chart.

Clinically significant ECG abnormalities detected at the screening visit should be recorded in the CRF as concomitant diseases. After that, all new, clinically significant ECG abnormalities should be registered as adverse events.

The ECG intervals (QT, RR, and QTcF) should be registered in the CRF for each ECG test.

CONFIDENTIAL P. 64 of 84

## 11.5.6 Laboratory blood tests

# Complete blood count

Complete blood count is carried out by the local laboratory of the study site in accordance with the procedure adopted by the site laboratory. A complete blood count involves assessment of the following peripheral blood parameters:

- Hemoglobin
- Hematocrit
- Erythrocytes
- Platelet count
- Total white blood cell count
- Absolute neutrophil count
- White blood cell differential in relative units:
  - Neutrophils (%)
  - Segmented neutrophils (%)
  - Stabs (%)
  - Eosinophils (%)
  - Basophils (%)
  - Monocytes (%)
  - Lymphocytes (%)

Blood chemistry, blood lipids, coagulation tests

Blood tests are carried out in the central laboratory, except for creatinine. Blood samples are collected under fasting conditions or before the patient receives the investigational product. Sample handling procedures for assessing blood chemistry, blood lipids, and coagulation are described in the laboratory manual.

The blood chemistry will include the following tests:

- Sodium
- Potassium
- Chloride
- Magnesium
- Calcium
- Phosphorus
- Bicarbonates
- Blood urea nitrogen (or urea)
- Uric acid
- Total protein
- Albumin
- Glucose
- Creatinine (local laboratory) with determination of creatinine clearance using the Cockcroft-Gault formula

• Total bilirubin

CONFIDENTIAL P. 65 of 84

- Direct bilirubin
- AST
- ALT
- Alkaline phosphatase
- Lactate dehydrogenase
- Amylase
- Lipase
- GGT
- Creatine kinase
- MB-creatine kinase

Blood lipids include the following parameters:

- Low-density lipoprotein
- Triglycerides
- LDL
- HDL

Blood clotting tests includes the following parameters:

- Fibrinogen
- INR
- APTT

#### 11.5.7 Urinalysis

Urinalysis is carried out by the local laboratory of the study site in accordance with the procedure adopted by the site laboratory.

The following urinalysis parameters will be assessed:

Physical parameters:

- Color
- Transparency
- Specific gravity
- pH value or reaction (acidic, alkaline, neutral)

Biochemical parameters:

- Glucose
- Protein
- Ketone bodies
- Bilirubin
- Urobilinogen
- Nitrites

In addition, information on the results of the analysis of sediment microscopy is recorded (leukocyte count, erythrocyte count, epithelial cell count with cell type, and bacterial count). Epithelial cell count with an indication of the cell type and bacterial count will be assessed as the presence or absence in the analysis.

CONFIDENTIAL P. 66 of 84

#### 12 ADVERSE EVENTS

In this study, an **adverse event** (AE) means any untoward medical event in a patient receiving the study drug that does not necessarily have a causal relationship with the drug. Thus, an adverse event can be any unintended and untoward symptom (for example, a laboratory abnormality), a symptom or a disease with temporal relationship with the use of the drug, regardless of whether they are considered to be related with the drug.

Clinical signs of treatment failure are not adverse events. For example, persistent pain or swelling in an affected joint should not be reported as an adverse event.

Symptoms, syndromes, and diseases noted prior to the study therapy, but after the patient signed the informed consent form, are recorded in the CRF as Concomitant Diseases.

Laboratory and investigation abnormalities should be registered as adverse events if these abnormalities are regarded by the investigator as clinically significant.

An **adverse drug reaction** is any adverse event with at least a possible (possible, probable, or certain) relationship with the use of the investigational medicinal product.

AE severity is graded according to the CTCAE classification v.5.0.

All adverse events should be monitored until resolution or stabilization (assessed by the investigator).

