#### 7.3 Exclusion criteria

Patients are not eligible for the study after the screening period if they meet any of the following criteria:

- 1. The patient received therapy with ibuprofen at a dose of up to 400 mg inclusive within 4 hours or >400 mg within 8 hours prior to the randomization;
- 2. The patient received therapy with diclofenac at a dose of up to 50 mg inclusive within 8 hours or >50 mg within 24 hours prior to the randomization;
- 3. The patient received any other non-steroidal anti-inflammatory drug (NSAID) within 24 hours prior to the randomization;
- 4. The patient received opioids within 48 hours prior to the randomization;
- 5. The patient received metamizole or metamizole-containing drugs within 12 hours prior to the randomization;
- 6. The patient received any analgesic drug (including paracetamol) within 6 hours prior to the randomization;
- 7. The patient received a long-acting NSAID (half-life ≥24 hours) within 5 half-life periods or 1 month prior to the randomization, whichever is longer;
- 8. The patient received naproxen, meloxicam, nabumetone, celecoxib, etoricoxib or extended-release indomethacin within 5 days prior to the randomization;
- 9. The patient received corticosteroids (including intra-articular and inhaled) within 4 weeks prior to the randomization;
- 10. The patient received colchicine within 7 days prior to the randomization;
- 11. Intolerance of or contraindications to NSAIDs;
- 12. Contraindications to Ortanol® capsules 20 mg;
- 13. Chronic heart failure, NYHA functional class II-IV;
- 14. A history of or current clinically significant ventricular arrhythmias or clinically significant atrial tachyarrhythmias;
- 15. Unstable angina or stable exercise-induced angina, functional class III or IV;
- 16. Secondary gout, chemotherapy-induced gout, lead- or transplantation-induced gout;
- 17. Rheumatoid arthritis, confirmed or suspected infectious septic arthritis or any other type of acute inflammatory arthritis;
- 18. Clinically significant renal impairment determined based on creatinine clearance (estimated using the Cockcroft-Gault formula) <60 mL/min, or patients on hemodialysis;
- 19. Blood coagulation disorders; a history of gastrointestinal bleedings or perforation;
- 20. Pregnant or breast-feeding women;

CONFIDENTIAL P. 39 of 84

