## 12.4 Serious adverse events (SAEs)

A serious adverse event (SAE) is any adverse event that meets one or more of the criteria listed below:

- 1. Resulted in the patient's death
- 2. Is life-threatening
- 3. Requires hospitalization or prolongation of existing hospitalization
- 4. Resulted in persistent or significant disability or incapacity
- 5. Is a congenital anomaly or developmental defect occurring in children born to patients treated with the investigational drug.

In addition, serious adverse events may include other important medical manifestations if the investigator believes, on the basis of his/her medical experience, that this manifestation may result in one of the outcomes described above if no medical intervention is undertaken.

An adverse event is considered to be "life-threatening" if the patient is at an immediate risk of death at the time of the event. This category does not include adverse events, which hypothetically might have caused the patient's death if they were more severe.

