# 12.5 SAE reporting procedure

To ensure safety for study subjects in case of any SAE developing after the patient signs the Informed Consent Form and before the end of the study, regardless of the suspected causes of the SAE or the relationship with the use of the investigational product, the SAE should be reported to the study Sponsor within 24 hours after the investigator becomes aware of the SAE.

If a study subject is found to develop a serious adverse event related to the use of the investigational product, it should be reported even if the study has already been completed.

Filling out the serious adverse event reporting form.

SAEs should be reported by sending a scanned copy of the completed Serious Adverse Event Reporting Form in paper format by e-mail to

CONFIDENTIAL P. 69 of 84

[contact].

or by [contact]

The primary contact for any issues related to the safety of the medicinal product is the Head of the Department of Drug Safety at R-Pharm JSC, Candidate of Medical Sciences, [name].

[contact] [name]

Mob. [contact]

[contact]

email: [contact]; [contact]

The Investigator must notify the LEC about SAEs in accordance with the LEC standard operating procedures.

The Study Sponsor must notify the regulatory authorities of the Russian Federation of all suspected unexpected serious adverse reactions within the time frame specified by the Russian law. In the context of notifying regulatory authorities and investigators, suspected unexpected serious adverse reactions will be deemed to be unexpected serious adverse events assessed by the investigator and/or Sponsor to be doubtfully, possibly, probably, or certainly related to the investigational therapy.

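### The treatment-failure exclusion in section 12 has no exception for seriousness, so an admission for persistent pain or swelling of an affected joint falls outside SAE reporting as written

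*Combined protocol and SAP*

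**What the plan says.** Section 12 opens with a broad definition. An AE is "any untoward medical event in a patient receiving the study drug that does not necessarily have a causal relationship with the drug", and this includes diseases that arise in time with treatment. It then sets a class of events aside: "Clinical signs of treatment failure are not adverse events". The illustration is an instruction to sites: "For example, persistent pain or swelling in an affected joint should not be reported as an adverse event".

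The sections that follow build on that definition:

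- Section 12.1 asks for a diagnosis rather than a list of symptoms.
- Section 12.2 names the natural course of the primary disease among the alternative causes to weigh for an AE.
- Section 12.4 states: "A serious adverse event (SAE) is any adverse event that meets one or more of the criteria listed below". One criterion is "Requires hospitalization or prolongation of existing hospitalization". A further paragraph adds that "serious adverse events may include other important medical manifestations if the investigator believes" they could lead to one of the listed outcomes without intervention.
- Section 12.5 requires a report to the sponsor within 24 hours, "regardless of the suspected causes of the SAE".
- Section 13.6.1 summarises AEs and lists SAEs from what was recorded as such.

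Two other places bear on the point. Exclusion criterion 17 in section 7.3 covers "confirmed or suspected infectious septic arthritis or any other type of acute inflammatory arthritis", so joint infection is treated as a condition distinct from the gout attack. Note 27 to Table 3.1 lets the investigator keep patients in hospital for observation after dosing.

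**The concern.** The exclusion acts on the AE definition itself, and everything downstream depends on that definition. If a sign is not an AE, the seriousness criteria are never applied to it, and the duty to report whatever the cause is never triggered. A patient admitted because the joint stays painful and swollen would then be missing from the AE tables, the SAE listing and expedited reporting.

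This matters here for three reasons. The study title puts safety first. RPH-104 binds IL-1β and the rescue drug is a corticosteroid (sections 4.2.1 and 9.8.2), so infection is a natural safety question, and a swollen, painful joint can be gout or infection. The trial is also open-label (section 6.3.2), so whoever decides between treatment failure and adverse event knows the drug and the dose.

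**Working it through.** The plan gives no figure to reproduce. The check is a reading of sections 12 to 12.5 together, with a search for an exception elsewhere.

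1. **Is the exclusion qualified?** No. Section 12 attaches no condition on seriousness, hospitalisation or suspected infection. None was found in the notes to Table 3.1 or in sections 6.2, 7.3, 8.1, 9.8.2, 10.5, 11.5.2 or 13.6.1.
2. **Can something be an SAE without being an AE?** By the definition in 12.4, no. The only other route is the paragraph on important medical manifestations, which is permissive and rests on the investigator's opinion.
3. **Does section 12.5 repair this?** No. It disregards cause, but it starts from an SAE.
4. **Do the sections agree on gout-related events?** Not fully. Section 12.2 allows the primary disease to be the cause of an AE, while section 12 removes part of that class beforehand.

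Applied to the cases that can arise:

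| Case | Result as written |
|---|---|
| Persistent pain or swelling, no admission | Not an AE; a defensible choice |
| Same signs, with unplanned or prolonged admission | Not an AE, so not an SAE, unless the discretionary clause is used |
| Joint worsens | Not named; the example speaks only of persistence |
| Joint infection diagnosed | AE under the general definition; SAE if a criterion is met |
| Infection suspected, no diagnosis yet | No instruction; may be attributed to treatment failure |
| Day 1 admission for observation under note 27 | 12.4 does not say how it counts |

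**Scale of one event.** In a planned group of 14, 1/14 = 7.1%. In the 4 mg group, 1/15 = 6.7%.

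The interim analysis covers 47 patients, and section 4 says its report may become final. Assume that Period 1 filled its 22 places and that the rest followed the 2:2:2:2:1 ratio; the documents do not state the actual split. Then 47 − 22 = 25 patients remain, 25 × 2/9 = 5.6 per higher-dose group, and one event is 1/5.6 = about 18%. These figures show what a single event would do to a proportion. They do not estimate how often it happens.

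**The case against.** Keeping signs of the index attack out of the AE tables is a legitimate choice, because it avoids counting lack of efficacy twice. Those signs are recorded elsewhere:

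- pain on the VAS at 19 post-dose times up to Day 45;
- physician-rated swelling, tenderness, erythema and movement from 24 hours to Day 45;
- every use of rescue, with time and dose;
- the reason for and findings of any unscheduled visit.

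Clinically significant changes in vital signs and laboratory values are AEs in their own right.

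This answers the worry about lack of effect by dose. It does not answer the worry about serious events, because none of these records starts the 24-hour route or enters the SAE listing. The efficacy tables are also a limited substitute: under section 13.1.6, readings after rescue are treated as missing and replaced by the baseline value in the main analysis.

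A reader might infer three stronger things that the documents do not support:

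- **That an infected joint need not be reported.** Infection is a new disease under the general definition, section 7.3 separates it from gout, and section 12.1 prefers the diagnosis to the symptom. What remains is misattribution before a diagnosis is made.
- **That a worsening joint is excluded.** The example is limited to persistence, and section 12.2 expects some gout-related events to be AEs. The text is silent here, not permissive.
- **That no such SAE could ever appear.** The discretionary paragraph in 12.4 leaves a way in.

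**Conclusion.** The gap is real but narrow. As written, an unplanned or prolonged hospitalisation for persistent pain or swelling of an affected joint falls outside AE and SAE recording and outside the 24-hour route, except at the investigator's discretion. For suspected but undiagnosed joint infection there is no instruction, and in an open-label trial the attribution could differ by arm; the documents do not show that it does.

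The frequency is unknown. The conclusion rests on the wording alone and on sites following section 12 literally. It should be corrected, because a stated rule can drop serious events from the safety tables of a small trial. It does not invalidate the safety analysis as a whole.

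**What to change.** Reconcile sections 12, 12.2 and 12.4 by adding to section 12:

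*Signs of the index attack are not adverse events unless they meet a seriousness criterion in section 12.4, or another diagnosis such as joint infection is suspected. In those cases they are recorded as adverse events and, where serious, reported under section 12.5. Admission for study observation on Day 1 (note 27 to Table 3.1) is not in itself a serious adverse event.*

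A further trigger for any sign worse than the patient's baseline is not advisable. Without a threshold, any of the 19 post-dose VAS readings a millimetre above baseline could become an AE and blur the safety tables.

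The 47 patients in the interim analysis have already completed participation. If that report becomes final, the amendment alone would not reach them, so their source records should be checked for joint-related admissions before the interim safety tables are closed.

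The cost is a short protocol amendment, site guidance, one check of existing records and a few more AE/SAE forms. The change affects reporting only; treatment is untouched.
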